#### **10.5.1.2 Standard Analyses for Ordinal Endpoints**

All ordinal endpoints will be summarized using the number and percent of subjects in each category by treatment group. Unless otherwise specified, the percentages will be based on the subjects with non-missing observations. Treatment comparisons on ordinal endpoints will be done using a repeated measures proportional odds model adjusting for age strata and presence or absence of severe vertebral fracture at baseline, visit and treatment by visit interaction. The odds ratios and their corresponding 95% 2-sided Wald confidence interval will be provided (SAS code in [Section 13.4.5](#)).

#### **10.5.1.3 Standard Analyses for Time-to-event Endpoints**

All time-to-event endpoints will be summarized descriptively using the Kaplan-Meier estimates at time point(s) of interest (SAS code in [Section 13.4.7](#)). Further analysis using a stratified Cox proportional hazards model controlling for age strata with presence or absence of severe vertebral fracture at baseline, baseline total hip BMD T-score, and treatment as the independent variable will also be provided (SAS code in [Section 13.4.8](#)). The significance of the treatment effect between treatment arm and control arm will be assessed based on the Cox proportional hazards model. The estimated hazard ratio, corresponding 95% confidence interval, and the p-value of the score test from the model will be provided. In addition, the point estimate of the adjusted risk difference (difference in Kaplan-Meier estimates at the time point of interest, control arm - treatment arm) and the corresponding 95% confidence interval will be provided

using the inverse variance-weighted method (SAS code in [Section 13.4.14](#)). For 12 months analysis, subjects without having the event of interest in the double-blind period will be censored at the end of double-blind period date. For 24 months analysis, subjects without having the event of interest in the study will be censored at the end of 24-month study period.

The proportional hazards assumption will be examined visually using log-log survival plots versus time and plots of Schoenfeld residuals versus time ([Schoenfeld, 1982](#)). If the proportional hazards assumption is violated, a piecewise Cox proportional hazards model assuming proportional hazards in the 1st year, the 2nd year, and all remaining years thereafter, will be used.

#### **10.5.1.4 Standard Analyses for Continuous Endpoints**

All continuous endpoints will be summarized using descriptive statistics including mean, standard deviation, minimum, 25th percentile, median (50th percentile), 75th percentile, maximum, and number of nonmissing observations (n).

#### **10.5.1.5 ANCOVA Model**

The ANCOVA model (SAS code in [Section 13.4.9](#)) will include treatment, age (stratification factor), presence or absence of severe vertebral fracture at baseline, and baseline value of the endpoint. The model will allow different variances for the treatment groups for DXA or QCT endpoints. Additional covariates of machine type and machine type-by-baseline value interaction will also be included in the model to adjust for the effect of machine type on baseline value for parameters derived by DXA. The age strata will not be included in analyses for the sub-study.

The least-squares mean of the treatment difference (treatment – control) and the corresponding 95% confidence interval will be summarized by time points of interest, where each time point is estimated using a separate ANCOVA model. Graphical display of the least-squares means by randomized treatment group across time points may also be provided to visually summarize the results from the model.

#### **10.5.1.6 Repeated Measures Model**

The likelihood-based repeated measures model ([Longford, 1993](#)) will include treatment, age strata (stratification factor), presence or absence of severe vertebral fracture at baseline, visit, baseline value of the endpoint, and treatment-by-visit interaction as fixed

effects using an unstructured variance-covariance structure. The model will allow different variances for the treatment groups for endpoints. Additional covariates of machine type (Hologic or Lunar) and machine type-by-baseline value interaction will also be included in the model to adjust for the effect of machine type on baseline value for parameters derived by DXA. The visit will be treated as a categorical variable. The age strata will not be included in analyses for the sub-study. The approach of [Kenward and Roger \(1997\)](#) for estimating the denominator degrees of freedom for the hypothesis test will be followed (SAS code in [Section 13.4.10](#)). Other variance-covariance structure may be substituted if convergence problem arises. The least-squares mean of the treatment difference (treatment – control) and the corresponding 95% confidence interval will be summarized by time points of interest. Graphical displays of least-squares means by randomized treatment group across time points may also be provided to visually summarize the results from the model.

#### **10.5.1.7 Wilcoxon Rank-sum Test**

Wilcoxon rank-sum test (SAS code in [Section 13.4.11](#)) will be used to assess the significance of the treatment difference at each time point for bone turnover markers and biomarkers and any other endpoints where parametric methods may not be appropriate.

#### **10.5.1.8 Van Elteren Stratified Rank Test**

Van Elteren stratified rank test (van Elteren, 1960; SAS code in [Section 13.4.13](#)) adjusting for age strata (stratification factor) and presence of severe vertebral fracture at baseline will be used to assess the significance of the treatment difference at each time point for continuous data from the main study where parametric methods may not be appropriate.

### **10.5.2 Analyses of Primary Efficacy Endpoints**

#### **10.5.2.1 Primary Analytical Approach**

The primary analytical model for comparing subject incidence of new vertebral fractures through Month 24 between the randomized treatment groups will use a logistic regression model as described in [Section 10.5.1.1](#) based on the primary efficacy analysis set for vertebral fractures as described in [Section 7.1](#). The number and percentage of subjects with  $\geq 1$  new vertebral fracture through Month 24 will be summarized by randomized treatment group. The adjusted odds ratio of romosozumab

as compared with ALN and the corresponding 95% confidence interval will also be provided.

The primary analytical model for comparing subject incidence of clinical fractures at primary analysis between the randomized treatment groups will use a stratified Cox proportional hazards model as described in [Section 10.5.1.3](#) based on the full analysis set as described in [Section 7.2](#). The cumulative incidence of fractures will be summarized using the Kaplan-Meier estimates, and the hazard ratios of romosozumab as compared with ALN and the confidence intervals for the risk reduction relative to ALN control arm will be based on the model.

#### **10.5.2.2 Supportive Analyses**

To demonstrate the robustness of the results from the primary analytical models, additional supportive analyses will be performed:

##### Per protocol analyses

Primary analytical models will be repeated using the per protocol subset as described in [Section 7.4](#) for new vertebral fracture through Month 24 and clinical fracture at primary analysis. For subjects who received the investigational product not matching their randomized treatment group or proscribed therapy on study and had investigational product IPD, their vertebral fracture evaluations will be ignored at or after the first occurrence of violation. The imputation described in [Section 9.2.2](#) will be used to impute their new vertebral fracture status at Month 24.

##### Time-to-event analysis based on full analysis set

A supportive analysis for new vertebral fracture through Month 24 will be performed based on time-to-first new vertebral fracture using the stratified Cox proportional hazards model as described in [Section 10.5.1.3](#).

#### **10.5.2.3 Covariate Analysis**

For new vertebral fracture the odds ratio of romosozumab as compared with ALN and corresponding 95% confidence interval and p-value, adjusting for each of the covariates listed in [Section 4.6](#) using the logistic regression model as described in [Section 10.5.1.1](#), as well as adjusting for all covariates simultaneously in a multivariate analysis, will be presented. The analysis subset and the imputation method will be the same as those used in the primary analytical model.

Similarly, for clinical fracture, the adjusted hazard ratio of romosozumab as compared with ALN and corresponding 95% confidence interval and p-value adjusting for each of the covariates listed in [Section 4.6](#) using the stratified Cox proportional hazards model as described in [Section 10.5.1.3](#), as well as adjusting for all covariates simultaneously in a multiple regression analysis, will be presented.

#### **10.5.2.4 Subgroup Analysis**

To assess the consistency of the treatment effect in different subgroups, the incidence of new vertebral fractures and incidence of clinical fracture will be analyzed within each subgroup stratum listed in [Section 7.9](#). For incidence of new vertebral fracture, the odds ratio of romosozumab as compared with ALN, and their respective 95% confidence intervals, will also be summarized for each category of a subgroup. The treatment-by-subgroup interaction will be tested using a logistic regression as described in [Section 10.5.1.1](#) and including individual subgroup and treatment-by-subgroup interaction. If the p-value of the interaction is  $\geq 0.05$ , the treatment-by-subgroup interaction is considered not significant. Otherwise, a 2-sided Gail and Simon test ([Gail and Simon, 1985](#)) will be used to test whether there is qualitative interaction (SAS code in [Section 13.4.6](#)).

For clinical fracture, the hazard ratio of romosozumab as compared with ALN, and their respective 95% confidence intervals, will also be summarized for each category of a subgroup. The treatment-by-subgroup interaction will be tested using stratified Cox proportional hazards model as described in [Section 10.5.1.3](#) and individual subgroup and treatment-by-subgroup interaction. Similarly, the interaction will be further evaluated for qualitative interaction using Gail and Simon test if the p-value of the score test for the interaction is  $\geq 0.05$ .

The verified age will be used to stratify subgroups for the analysis of age subgroup.

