## 7.9 Subgroup Analyses

The new vertebral fracture through Month 12 or Month 24, clinical fracture and nonvertebral fracture through Month 12 or at primary analysis, will be analyzed within each of the following subgroups:

- Age ( $< 75$  years,  $\geq 75$  years)
- Presence or absence of severe vertebral fracture at baseline (based on most severe Genant semiquantitative grade at baseline on screening spinal radiograph)
- Number of prevalent vertebral fractures at baseline (0-1, 2,  $\geq 3$ ; based on screening spinal radiograph)
- Race (White and non-White)
- Geographic region
  - Western Europe and New Zealand/Australia
  - Central and Eastern Europe and Middle East
  - Asia Pacific and South Africa
  - North America
  - Central/Latin America
- Central/Latin America and all regions excluding Central/Latin America
- Baseline lumbar spine BMD T-score ( $\leq -3$ ,  $> -3$  and  $\leq -2.5$ ,  $> -2.5$ )
- Baseline total hip or femoral neck BMD T-score  $\leq -3$  vs both total hip and femoral BMD T-score  $> -3$

- Baseline BMI (tertiles)
- FRAX score for major osteoporotic fracture (tertiles)
- History of nonvertebral fracture at age  $\geq 55$  years (yes, no)

The percent changes from baseline in lumbar spine BMD and total hip BMD at month 12 and month 24 will be analyzed by the following subgroups:

- Age ( $< 75$  years,  $\geq 75$  years)
- Geographic region
- Baseline lumbar spine BMD T-score ( $\leq -3$ ,  $> -3$  and  $\leq -2.5$ ,  $> -2.5$ ; for lumbar spine BMD analysis only)
- Baseline total hip BMD T-score ( $\leq -3$ ,  $> -3$  and  $\leq -2.5$ ,  $> -2.5$ ; for total hip BMD analysis only)

These subgroups, except for age strata, will be re-examined for appropriateness and may be re-categorized or omitted (due to small sample size, for example, if there are  $< 10\%$  of subjects within a subgroup) before unblinding. The analyses of these subgroups will be exploratory in nature.

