For nonvertebral fracture through Month 12 and at primary analysis, the hazard ratio of romosozumab as compared with ALN, and their respective 95% confidence intervals, will also be summarized for each category of a subgroup. The treatment-by-subgroup interaction will be tested using stratified Cox proportional hazards model as described in [Section 10.5.1.3](#) and individual subgroup and treatment-by-subgroup interaction. Similarly, the interaction will be further evaluated for qualitative interaction using Gail and Simon test if the p-value of the score test for the interaction is  $\geq 0.05$ .

The efficacy analysis set in Month 12 to 24 study period as described in [Section 7.10](#) will be used for the analyses of following efficacy endpoints between Month 12 and Month 24: subject incidence of clinical fracture, subject incidence of nonvertebral fracture, subject incidence of hip fracture, and subject incidence of clinical vertebral fracture. The incidence of fractures will be summarized using the Kaplan-Meier estimates, and the hazard ratios of romosozumab as compared with ALN and the confidence intervals will be based on the stratified Cox proportional hazards model as described in

[Section 10.5.1.3](#). Due to the lack of randomization at Month 12, the comparability between the two arms is not ensured and therefore the analysis is more susceptible to bias.

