## 11. Changes From Protocol-Specified Analyses

Protocol [Section 10.5.2.1](#) specified a logistic regression model adjusting for fracture location and potentially other factors impacting the pain score to analyze the incidence of subjects with a clinical meaningful improvement in worst pain. Fracture type is used as a covariate instead of the fracture location.

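### The Gail-Simon trigger for clinical and nonvertebral fracture subgroups is reversed: the SAP runs the test when the interaction is not significant and skips it when it is

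*SAP*

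**What the plan says.** SAP 10.5.2.4 sets two rules for following up a treatment-by-subgroup interaction.

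- **New vertebral fracture (logistic model).** If the interaction p-value is ≥ 0.05, "the treatment-by-subgroup interaction is considered not significant". The next sentence begins "Otherwise, a 2-sided Gail and Simon test", so Gail-Simon is used at p < 0.05.
- **Clinical fracture (stratified Cox model).** Opening with the word *Similarly*, the SAP says "the interaction will be further evaluated for qualitative interaction using Gail and Simon test if the p-value of the score test". The condition that completes this sentence is a value of 0.05 or higher.

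SAP 10.5.3.1 repeats the second rule, with the same opening word and the same sign, for nonvertebral fracture through Month 12 and at primary analysis. There the hazard ratios and 95% confidence intervals "will also be summarized for each category of a subgroup" whichever way the interaction test falls.

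SAP 7.9 lists the subgroups and says "The analyses of these subgroups will be exploratory in nature". The protocol does not mention Gail-Simon, so the SAP is the only source for the rule.

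**The concern.** The two Cox-model rules are the exact complement of the logistic rule that they claim to follow. Gail-Simon asks whether a treatment effect changes direction between categories. That question arises once the effects appear to differ, so the usual order is an interaction test first and Gail-Simon only if it is significant. With the sign reversed, the formal test is withheld in the cases it exists for and produced in the cases where it has nothing to add.

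What is at stake is the formal qualitative-interaction p-value for clinical fracture (one of the two primary endpoints) and for nonvertebral fracture, and consistent handling of the three fracture endpoints. A programmer who follows the text gets the rule backwards. One who quietly corrects it departs from the SAP without a record.

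**Working it through.** **1. The rules side by side**

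| Endpoint | SAP section | Gail-Simon is run when interaction p is |
|---|---|---|
| New vertebral fracture | 10.5.2.4 | < 0.05 |
| Clinical fracture | 10.5.2.4 | ≥ 0.05 |
| Nonvertebral fracture (Month 12, primary analysis) | 10.5.3.1 | ≥ 0.05 |

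The same sign stands in two separate sentences, and it reads correctly in the vertebral fracture sentence, so a PDF reading fault is unlikely.

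**2. How many tests are affected**

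Section 7.9 lists 11 subgroup factors for fracture.

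- Six have 2 categories: age, severe vertebral fracture, race, Central/Latin America versus the rest, hip/femoral neck T-score, and nonvertebral fracture history.
- Four have 3: number of prevalent fractures, lumbar spine T-score, BMI and FRAX.
- One has 5: region.

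Clinical fracture at primary analysis plus nonvertebral fracture at two time points gives 11 × 3 = 33 interaction tests. If clinical fracture through Month 12 follows the same rule, the count is 11 × 4 = 44. These are maxima, because 7.9 says that subgroups other than age "will be re-examined for appropriateness and may be re-categorized or omitted (due to small sample size, for example, if there are" fewer than 10% of subjects in one.

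**3. Can Gail-Simon reject when the interaction p is ≥ 0.05?**

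The SAP gives no level for Gail-Simon; 0.05 is assumed. The test rejects when both the positive-sign and the negative-sign sums of squared z-values exceed a critical value c. At 0.05, c is 2.71, 4.23 and 6.50 for K = 2, 3 and 5 categories.

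Let the categories of one sign hold a share q of the statistical information. The smallest interaction chi-square compatible with rejection is then

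c × (√q + √(1−q))² = c × (1 + 2√(q(1−q))), on K − 1 degrees of freedom.

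| | K = 2 | K = 3 | K = 5 |
|---|---|---|---|
| Chi-square cut-off for interaction p = 0.05 | 3.84 | 5.99 | 9.49 |
| Equal categories, smallest share q | 1/2 | 1/3 | 1/5 |
| Minimum chi-square (largest p) | 5.41 (0.020) | 8.22 (0.016) | 11.70 (0.020) |
| Smallest share q = 0.10: 1.6 × c (largest p) | 4.33 (0.037) | 6.77 (0.034) | 10.40 (0.034) |
| Share q below which rejection at p ≥ 0.05 becomes possible | 4.6% | 4.5% | 5.6% |

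So a Gail-Simon rejection implies an interaction p below 0.05 unless the categories of one sign hold only about 5% of the information or less. The 10% row is an assumption that borrows the 10%-of-subjects example in 7.9.

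**4. An example on the plan's scale**

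Take 396 clinical fractures, the simulated median in SAP 3.2.3, split equally over two categories of 198.

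- SE(log HR) = √(4/198) = 0.142 in each category.
- Gail-Simon starts to reject at |z| = √2.71 = 1.645 with opposite signs: exp(−1.645 × 0.142) = 0.79 and exp(+1.645 × 0.142) = 1.26.
- Interaction z = 2 × 1.645/√2 = 2.33, p = 0.020.

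At that borderline the written rule would not run the test.

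**5. Simulation**

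Two categories, 330 events (the trigger for the primary analysis), 1,000,000 replicates per scenario, SE = 2/√events:

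- With HR 0.70 in both categories, the written rule runs Gail-Simon in 95% of replicates; the corrected rule does so in 5%.
- With HR 0.5 versus 1.5, the written rule detects the reversal in 0% of replicates for event splits of 50:50, 30:70 and 10:90. The corrected rule detects it in 83%, 89% and 61%.

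**The case against.** The strongest reply is that this is a sign slip with an obvious intended reading. *Similarly* points back to the correct rule, the analyses are exploratory, and the hazard ratios, confidence intervals and interaction tests appear either way. With no true interaction, only about 5% of 33 tests, or 1 to 2, would be skipped under the literal text. The Gail-Simon code in Section 13.4.6 is not visible in the public SAP, so the programmed rule may already be right. All of this stands, and it limits the consequence. It does not make the written rule correct.

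Two technical objections also have force. First, the result that Gail-Simon cannot reject is conditional. Section 7.9 permits small categories to be merged or dropped but does not require it, and its 10% example counts subjects, not information, so a very small category could be an exception. The bounds are also Wald approximations, whereas the SAP uses a score test from an adjusted, stratified Cox model. Second, the result depends on the assumed 0.05 level. At 0.10 with two equal categories, c = 1.64 and the bound is 3.28 (p = 0.07), so the written rule could then give a positive test. Even so, it would still skip every significant interaction.

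Section 11 of the SAP does not mention the difference, but that section records departures from the protocol, and the protocol has no Gail-Simon rule. Little should be made of its silence.

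**Conclusion.** The concern holds. The SAP states opposite triggers for the same test, and nothing in either document reconciles them. The reversal itself is plain from the text and needs no assumption. The finding that the test is then run almost only where it cannot reject assumes a Gail-Simon level of 0.05, a Wald approximation, and no set of same-sign categories holding less than about 5% of the information.

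Up to 33 exploratory tests (44 on the wider reading) are affected. A reversal of effect relative to alendronate would remain visible in the category-level hazard ratios. What is lost is the formal p-value when it could be informative, and consistent treatment of the fracture endpoints. Primary inference, alpha and sample size do not change. This should be corrected, but it does not threaten the trial's conclusions.

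**What to change.** Change ≥ 0.05 to < 0.05 in the clinical fracture sentence of SAP 10.5.2.4 and in the nonvertebral fracture sentence of 10.5.3.1. In the same edit, state the significance level for Gail-Simon and say whether clinical fracture through Month 12, listed in 7.9, follows the same rule. Confirm that the code in Section 13.4.6 and the logic that calls it apply the corrected trigger to all three fracture endpoints.

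The cost is one sign in each of two sentences, a short clarification and a program check, best done before unblinding. No new data or analyses are needed.

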#### **10.5.3 Analyses of Secondary and Exploratory Efficacy Endpoints**

##### **10.5.3.1 Nonvertebral Fracture, Clinical Fracture, Clinical Vertebral Fracture, All Fracture, Major Nonvertebral Fracture, Major Osteoporotic Fracture and Hip Fracture**

The full analysis set as described in [Section 7.2](#) will be used for the analyses of following efficacy endpoints:

- subject incidence of nonvertebral fracture through Month 12, through Month 24, at primary analysis and final analysis
- subject incidence of clinical fracture through Month 12 and through Month 24

- subject incidence of clinical vertebral fracture through Month 12 and through Month 24
- subject incidence of all fracture through Month 12 and at primary analysis
- subject incidence of major nonvertebral fracture through Month 12, at primary analysis and at final analysis
- subject incidence of major osteoporotic fracture through Month 12 and at primary analysis
- subject incidence of hip fracture through Month 12, through Month 24, at primary analysis and at final analysis.

As described in [Section 10.5.1.3](#), the cumulative incidence of fractures will be summarized using the Kaplan-Meier estimates, and the hazard ratios of romosozumab as compared with ALN and the confidence intervals will be based on the stratified Cox proportional hazards model.

The primary analytical model for clinical fracture through Month 12, nonvertebral fracture through Month 12, at primary and final analyses, will be repeated using the per protocol subset as described in [Section 7.3](#) and [7.4](#) as a supportive analysis. Further, the hazard ratio and corresponding 95% confidence interval and p-value adjusting for each of the covariates listed in [Section 4.6](#) using the stratified Cox proportional hazards model as described in [Section 10.5.1.3](#), as well as adjusting for all covariates simultaneously in a multiple regression analysis, will be presented.

For nonvertebral fracture through Month 12 and at primary analysis, the hazard ratio of romosozumab as compared with ALN, and their respective 95% confidence intervals, will also be summarized for each category of a subgroup. The treatment-by-subgroup interaction will be tested using stratified Cox proportional hazards model as described in [Section 10.5.1.3](#) and individual subgroup and treatment-by-subgroup interaction. Similarly, the interaction will be further evaluated for qualitative interaction using Gail and Simon test if the p-value of the score test for the interaction is  $\geq 0.05$ .

The efficacy analysis set in Month 12 to 24 study period as described in [Section 7.10](#) will be used for the analyses of following efficacy endpoints between Month 12 and Month 24: subject incidence of clinical fracture, subject incidence of nonvertebral fracture, subject incidence of hip fracture, and subject incidence of clinical vertebral fracture. The incidence of fractures will be summarized using the Kaplan-Meier estimates, and the hazard ratios of romosozumab as compared with ALN and the confidence intervals will be based on the stratified Cox proportional hazards model as described in

[Section 10.5.1.3](#). Due to the lack of randomization at Month 12, the comparability between the two arms is not ensured and therefore the analysis is more susceptible to bias.

